## **7. Procedures Involved**

Informed consent will be obtained by an IRB-approved member of the study staff. The process of informed consent will begin with a verbal description of the experimental tasks. Participants will then have an opportunity to read the informed consent form that explains in more detail the requirements for participation, including protections of privacy and confidentiality. Participants will be told of their rights to discontinue participation at any time and that there will be no immediate benefit to participating and no disadvantage to discontinuing. Participants will be given contact numbers for the PI and the Executive Director of the Human Research Protection Office should they have

any questions or concerns regarding their participation. Informed consent documentation will take place in a private setting convenient to the participant.

Once the consent is obtained, the patient will undergo sweat testing. The testing will be performed with the subject resting comfortably on a chair and total duration of testing will be 45 minutes. The right forearm will be used for pilocarpine iontophoresis and the left forearm will be used for microneedle-based stimulation for a period of 5 minutes. A control microneedle patch without pilocarpine will also be placed on the left forearm to assess for any microneedle patch related changes. After the stimulation phase, collection of sweat will be performed on each forearm simultaneously for a period of 30 minutes (excluding the control microneedle patch site). At the end of the 30-minute sweat collection period, the collection device will be removed and the study visit will be completed. All the collected sweat samples (2 for each subject) will be frozen for later analysis of the sweat volume and chloride concentration.

The pilocarpine microneedles that will be used for the experimental procedure will be manufactured at Global Center for Medical Innovation (GCMI). This is not part of Georgia Tech. It is an independent institution. The pilocarpine-loaded MN patches are fabricated by a two-step molding process using polydimethylsiloxane (PDMS) molds with some modification on an established method. The first casting solution is a mixture of 10% (w/v) pilocarpine nitrate, 10% (w/v) poly (vinyl alcohol) and 5% (w/v) sucrose, which is prepared by mixing the different components in water at the desired ratio. This solution is then cast on PDMS molds under vacuum to facilitate filling the solution into the molds. After 20 min, excess solution is removed, and the filled molds are centrifuged at 5000 rpm for 20 min to dry the drug loaded MNs. The second casting solution containing 20% (w/w) polystyrene in 1, 4-dioxane is then cast on the filled PDMS molds under vacuum. The mold is kept under vacuum for another 3 h to dry the solution at room temperature, and then further dried at 40°C overnight before demolding the MN patches by adhesive tape. Each patch is immediately stored with desiccant in individual sealed pouches prior until use.

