## 1. Study Summary

Study Title	A pilot study to compare the efficacy of Pilocarpine Microneedles with iontophoresis method for sweat induction in healthy human subjects
Study Design	Phase 1 Clinical Pilot study – cross sectional
Primary Objective	To compare the sweat volume from application of Pilocarpine Microneedle patch to the forearm of healthy adult subjects with that of standard of care method using pilocarpine iontophoresis
Secondary Objective(s)	To measure the sweat chloride concentrations from the sweat samples obtained from the application of Pilocarpine Microneedle patch to the forearm of healthy adult subjects and compare them with measurements from standard of care method using pilocarpine iontophoresis
Research Intervention(s)/Interactions	To perform sweat testing on forearms with standard pilocarpine iontophoresis method and microneedle patch method
Study Population	Healthy adults $\geq 18$ years of age
Sample Size	50 subjects
Study Duration for individual participants	1 day
Study Specific Abbreviations/ Definitions	AE – Adverse Event/Adverse Experience CF – Cystic Fibrosis CFR – Code of Federal Regulations CHOA – Children's Healthcare of Atlanta CTACE – Common Terminology Criteria for Adverse Events FDA – Food and Drug Administration GCP – Good Clinical Practice HIPAA – Health Insurance Portability and Accountability Act IB – Investigator's Brochure ICF – Informed Consent Form IRB – Institutional Review Board N – Number (typically refers to subjects) PHI – Protected Health Information PI – Principal Investigator REDCap – Research Electronic Data Capture SAE – Serious Adverse Event SOP – Standard Operating Procedure
Funding Source (if any)	Center for Cystic Fibrosis and Airway Inflammation Research (CF-AIR)

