## 2. Objectives

The main objective of this study is to demonstrate the safety and feasibility of using pilocarpine microneedles for sweat induction during the process of sweat testing in healthy human adult subjects ( $\geq 18$  years of age) and comparing it to the standard method of sweat induction (Pilocarpine iontophoresis) in terms of sweat volume collected and sweat chloride concentrations.

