## **6. Study Intervention/Investigational Agent**

The study involves the use of pilocarpine for its approved indication for sweat induction during the clinical procedure for sweat testing in human subjects. The pilocarpine will be administered in the form of an agar gel disc using iontophoresis (Standard Procedure) on one arm of the subject, while the other arm will receive pilocarpine microneedles (Experimental Procedure) without any iontophoresis. This will allow a direct comparison of the two methods in terms of the efficiency of induction of sweat production in human subjects and whether the sweat chloride concentrations in the sweat samples obtained by the two methods are comparable or not. In addition, a control microneedle patch without any Pilocarpine will be placed on the left forearm to assess the effect of the microneedle patch use. The subsequent steps for the collection of sweat after completing the induction will be done with the same method for both arms using a macrōduct collector at each site (Standard Procedure). There will be no sweat collection performed at the site the control microneedle patch. Pictures of the skin sites will be taken before and after the interventions at each site.

The study team will plan to enroll study subjects of all ethnicities or racial backgrounds, so that the impact of this intervention can be studied in individuals with different skin characteristics.

**Protocol Title:** A pilot study to compare the efficacy of Pilocarpine Microneedles with iontophoresis method for sweat induction in healthy human subjects

---

Because this study involves an approved drug (Pilocarpine) that has been in clinical use for application to the skin for the purpose of sweat testing, we think that this project will not require an Investigational New Drug (IND) application. This has been discussed at length with several regulatory experts and FDA and the conclusion of these discussions was that the drug component is exempt from an IND under 21 CFR 312.2(b), and the device component is exempt from an IDE under 21 CFR 812.2(b), since all the related conditions in those two provisions are met by our device and study design.

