## **18. Data Management and Confidentiality**

Descriptive analysis will be conducted for the study participants to describe their clinical presentation and long-term outcomes. Several steps will be taken to secure the data by ensuring adequate training of the study team members, authorization of access to the study team for the clinical data, password protection, encryption, and separation of identifiers and data during the storage, use, and transmission. Data will be stored on each users' secure servers and not downloaded to external devices, including laptops. The information, even if de-identified, will be destroyed at the expiration of the project.

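### Iontophoresis is always on the right forearm and the microneedle patch always on the left, so a mean right-left difference cannot be separated from the method difference

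*Combined protocol and SAP*

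**What the plan says.** Section 7 (Procedures Involved) fixes the layout without exception: "The right forearm will be used for pilocarpine iontophoresis and the left forearm will be used for microneedle-based stimulation". Section 6 speaks only of one arm and the other arm, but it puts the drug-free control patch on the left, which agrees with Section 7.

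The comparison between arms carries both efficacy aims. The primary objective in Section 1 is "To compare the sweat volume from application of Pilocarpine Microneedle patch to the forearm of healthy adult subjects" with that from iontophoresis, and the secondary objective makes the same comparison for chloride. Section 6 says of the two-arm layout: "This will allow a direct comparison of the two methods in terms of the efficiency of induction of sweat production in human subjects". It expects the same layout to show "whether the sweat chloride concentrations in the sweat samples obtained by the two methods are comparable or not".

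Section 2 puts the emphasis elsewhere: "The main objective of this study is to demonstrate the safety and feasibility of using pilocarpine microneedles for sweat induction". The only analysis named is in Section 18: "Descriptive analysis will be conducted for the study participants". No section randomises, alternates or counterbalances side, mentions hand dominance, or gives a reason for fixing the side.

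**The concern.** Testing both methods in the same person removes differences between people. It does not remove a consistent difference between right and left forearms. When method and side coincide in every subject, such a difference goes straight into the estimated method effect. It could create an apparent difference between the methods or hide a real one, and the data could not show which.

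Only a systematic difference does this. Asymmetry that favours the right arm in some subjects and the left in others adds variance, not bias. An effect of hand dominance would be partly separable, but only if handedness were recorded and left-handers were enrolled.

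The bias sits in the mean difference itself, so it affects a purely descriptive estimate as much as a formal test. It cannot be corrected after the study, because the data will contain no variation in side.

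**Working it through.** The plan states no SD, effect size, alpha or power, so there is no figure of its own to reproduce. The one available count agrees: 10 + 40 = 50 subjects (Section 4).

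**Can the two effects be separated?**

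Inputs: 50 subjects (Sections 1 and 12); two samples per subject, one per forearm (Section 7); one visit (Section 10); no sweat collected at the control patch (Section 6); no change of side between the two phases (Section 4).

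The 100 samples call for 50 subject effects, a method effect and a side effect, which is 52 columns in the design matrix.

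- Side fixed: rank 51 of 52, because the method and side columns are identical. Only the sum of the two effects can be estimated.
- Side split 25/25: rank 52 of 52. Both effects are estimable, with zero covariance. The variance of the method effect is 0.04 times the within-subject residual variance, equal to the 2/50 = 0.04 of the fixed-side mean difference.

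**How much could it matter?**

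The documents do not give the mean side difference, so it is assumed here as d, in units of the SD of the paired difference. The illustration uses a t-based 95% confidence interval from 50 pairs. The plan does not specify such an interval.

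Coverage = P(|T| ≤ t(0.975, 49)), where T is non-central t with 49 df and non-centrality d√50, and t(0.975, 49) = 2.010. The result does not depend on the true method difference.

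| Assumed d | d√50 | Coverage, side fixed | Coverage, 25/25 with side term |
|---|---|---|---|
| 0 | 0 | 95.0% | 95% |
| 0.1 | 0.71 | 89.3% | 95% |
| 0.2 | 1.41 | 71.6% | 95% |
| 0.3 | 2.12 | 45.2% | 95% |

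Simulation with 200,000 runs, at true method differences of 0 and −0.5 SD, agrees to within 0.2 percentage points for the fixed side. It gives 94.95% to 95.06% for the randomised design.

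**What does balancing cost in precision?**

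Half-widths of the 95% interval, in SD units:

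- Side fixed: t(0.975, 49)/√50 = 2.0096/7.0711 = 0.2842.
- 25/25 with a side term: t(0.975, 48) × 0.5 × √(1/25 + 1/25) = 2.0106 × 0.5 × 0.2828 = 0.2843.
- 28/22, if balance slips: 2.0106 × 0.5 × √(1/28 + 1/22) = 0.2864.

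**Would recording handedness be enough?**

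With side still fixed and L left-handers (assumed counts), the dominance-adjusted half-width is 2.0106 × 0.5 × √(1/(50 − L) + 1/L). For L = 3, 5 and 8 it is 0.60, 0.47 and 0.39 SD, which is 2.11, 1.67 and 1.36 times 0.2842. A pure right-left effect would still remain in the estimate.

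**The case against.** The strongest reply is that no consequence has been shown. Nothing in the documents says that forearms differ on average in sweat volume or chloride, and if they do not, the bias is zero. The coverage table depends only on n = 50 and the assumed shift, so any study with 50 pairs would give the same rows. Because the SD is not stated, the shifts cannot be turned into a volume or a concentration. A smaller shift does little: on the same formula, 0.02 SD gives 94.8% coverage and 0.05 SD gives 93.6%. The study is also a pilot with safety and feasibility as its main objective and only a descriptive analysis, so no stated decision rule would change.

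This stands as a limit on severity. The size of the bias is unknown, and the table is an illustration. It does not remove the problem: the documents do not establish that the arms are equivalent, this design could not detect that they are not, and Section 1 makes the between-method volume comparison the primary objective.

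Three smaller points have some force. Section 8 lists no data fields, so handedness might be recorded without the protocol saying so; with side fixed, that would help only in part. Simple counterbalancing would also break the aliasing. A fixed side gives an easy link between site, photographs and the used-patch assay, and that is a real but small advantage.

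**Conclusion.** The concern holds. As planned, the mean paired difference estimates the method difference plus the mean right-left difference, for volume and for chloride, and nothing in the design can split the two. This follows from the layout alone and needs no assumption.

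The size of the bias equals the mean right-left difference. The documents do not give it, and it may be zero. Over the assumed range of 0 to 0.3 SD of the paired difference, coverage of a 95% interval falls from 95% to 45%.

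The safety and feasibility aims and the DSMB review are unaffected. The point should be fixed because the comparison is the primary objective, the remedy is cheap, and it works only if applied before subjects are tested.

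**What to change.** In Sections 6 and 7, replace the fixed side with wording such as: *The forearm that receives iontophoresis will be randomised per subject in balanced blocks (25 right, 25 left). The active and control microneedle patches will both go on the other forearm.* Blocks of even size can be chosen to fit the phases: 5/5 in the first 10 subjects and 20/20 in the next 40 give 25/25. A repeat cohort of 10 under a revised procedure could be split 5/5 as well.

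Record the side used and hand dominance in REDCap. For volume and for chloride, report the mean paired method difference with its 95% confidence interval from a model with side as a term.

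The cost is a randomisation list, two form fields, a protocol amendment through the IRB and one degree of freedom. No subjects, visits or samples are added. There is a small risk of confusing sites, which matters because the photographs and the used-patch assay depend on correct site identity. Labelling each site and showing the label in the photographs already planned in Section 6 ("Pictures of the skin sites will be taken before and after the interventions at each site") deals with it.

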## **8. Data and Specimen Banking**

Data for the study participants will be stored in the online REDCap (Research Electronic Data Capture) Database with only de-identified information being used for statistical analyses. REDCap is a secure, web-based application designed to support data capture for research studies, providing 1) an intuitive interface for validated data entry; 2) audit trails for tracking data manipulation and export procedures; 3) automated export procedures for seamless data downloads to common statistical packages; and 4) procedures for importing data from external sources. Access to this data will be limited to the study investigators only. Sweat samples may be stored frozen at Emory Children's Center for future tests. All the used microneedle patches will be sent to [name] lab to measure the amount of Pilocarpine delivered into the skin and then the patches will be destroyed as per the steps outlined in Appendix 8.

## **9. Sharing of Results with Participants**

The study team does not plan to share the results of the sweat sample collection. Sweat samples will be tested for chloride concentration and volume. The summary results will be posted on clinicaltrials.gov website.

## **10. Study Timelines**

Participants will only need to take part in one study visit totaling 45 minutes. The study team anticipates enrolling all study participants over the course of 6 months. Completion of all study related procedures, including data analysis, is expected to take approximately 12 months. No follow up visits will be needed for any of the study participants.

## **11. Inclusion and Exclusion Criteria**

### **Inclusion Criteria:**

- Age  $\geq 18$  years
- Signed a written informed consent
- Not taking any medications
- No known medical diagnoses or chronic conditions

### **Exclusion Criteria:**

- Age  $< 18$  years
- Family history of Cystic Fibrosis
- History of skin disorders (eczema, psoriasis etc.) that could prevent sweat testing on forearms
- Current medication use
- Pregnant women
- Breastfeeding women

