**Systemic:**

The following adverse drug reactions and incidences are derived from product labeling unless otherwise specified.

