**1% to 10%:**

Cardiovascular: Edema (<1% to 5%), facial edema, hypertension (3%), palpitation, tachycardia

Central nervous system: Pain (4%), fever, somnolence

Dermatologic: Pruritus, rash

Gastrointestinal: Diarrhea (4% to 7%), dyspepsia (7%), vomiting (3% to 4%), constipation, flatulence, glossitis, salivation increased, stomatitis, taste perversion

Genitourinary: Vaginitis, urinary incontinence

Neuromuscular & skeletal: Myalgias, tremor

Ocular: Lacrimation (6%), amblyopia (4%), abnormal vision, blurred vision, conjunctivitis

Otic: Tinnitus

Respiratory: Cough increased, dysphagia, epistaxis, sinusitis

Miscellaneous: Allergic reaction, voice alteration

**<1%:** Abnormal dreams, abnormal thinking, alopecia, angina pectoris, anorexia, anxiety, aphasia, appetite increased, arrhythmia, arthralgia, arthritis, bilirubinemia, body odor, bone disorder, bradycardia, breast pain, bronchitis, cataract, cholelithiasis, colitis, confusion, contact dermatitis, cyst, deafness, depression, dry eyes, dry mouth, dry skin, dyspnea, dysuria, ear pain, ECG abnormality, eczema, emotional lability, eructation, erythema nodosum, esophagitis, exfoliative dermatitis, eye hemorrhage, eye pain, gastritis, gastroenteritis, gastrointestinal disorder, gingivitis, glaucoma, hematuria,

**Protocol Title:** A pilot study to compare the efficacy of Pilocarpine Microneedles with iontophoresis method for sweat induction in healthy human subjects

---

hepatitis, herpes simplex, hiccup, hyperkinesias, hypoesthesia, hypoglycemia, hypotension, hypothermia, insomnia, intracranial hemorrhage, laryngismus, laryngitis, leg cramps, leukopenia, liver function test abnormal, lymphadenopathy, mastitis, melena, menorrhagia, metrorrhagia, migraine, moniliasis, myasthenia, MI, neck pain, photosensitivity reaction, nervousness, ovarian disorder, pancreatitis, paresthesia, parotid gland enlargement, peripheral edema, platelet abnormality, pneumonia, pyuria, salivary gland enlargement, salpingitis, seborrhea, skin ulcer, speech disorder, sputum increased, stridor, syncope, taste loss, tendon disorder, tenosynovitis, thrombocythemia, thrombocytopenia, thrombosis, tongue disorder, twitching, urethral pain, urinary impairment, urinary urgency, vaginal hemorrhage, vaginal moniliasis, vesiculobullous rash, WBC abnormality, yawning

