#### 4. Study Design

This is a cross sectional pilot study which will be conducted in a phased manner (Figure 4). The first phase of the study will include the enrollment of 10 healthy adult subjects who will undergo testing to assess the safety and efficacy of pilocarpine microneedle patch. The safety data from the first 10 subjects will be submitted to the Data and Safety Monitoring Board (DSMB) that will review the reported adverse events during testing. The DSMB will independently assess this safety data and provide their recommendations on whether it is safe to continue the study or not. These recommendations will be submitted to the Emory IRB. If there are no safety concerns reported by DSMB, then the second phase of the study will begin where the study team will continue enrollment of an additional 40 subjects to complete testing. After the enrollment and testing of 50 subjects, the study will be completed and another report of safety data will be submitted to the DSMB at the end of the study. The DSMB will review this final report and their final recommendations will be shared with Emory IRB and study team.

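### The eligibility criteria do not address a known hypersensitivity or earlier skin reaction to pilocarpine or to the patch or electrode materials

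*Combined protocol and SAP*

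**What the plan says.** Section 11 lists four inclusion and six exclusion criteria. Two bear on this point. The skin exclusion is "History of skin disorders (eczema, psoriasis etc.) that could prevent sweat testing on forearms". The general health inclusion criterion is "No known medical diagnoses or chronic conditions". The others concern age, consent, current medication, family history of cystic fibrosis, pregnancy and breastfeeding.

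Section 3 reproduces a list of adverse reactions to pilocarpine. In the 1% to 10% band it has "Dermatologic: Pruritus, rash" and "Miscellaneous: Allergic reaction, voice alteration"; contact dermatitis is in the band below 1%. The list stands under the heading for systemic effects, with this source note: "The following adverse drug reactions and incidences are derived from product labeling unless otherwise specified".

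Section 15 accepts that the patch may cause some hours of irritation or redness, and that iontophoresis may cause redness or, in some cases, welts.

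On exposure, Section 7 states: "The right forearm will be used for pilocarpine iontophoresis and the left forearm will be used for microneedle-based stimulation". It adds: "A control microneedle patch without pilocarpine will also be placed on the left forearm".

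**The concern.** The protocol names a hazard in Sections 3 and 15 and does not carry it into Section 11. A volunteer who already knows of a reaction to pilocarpine, or to a material in the patch or electrode, is the person for whom a further reaction is most foreseeable. One question would identify that person, and the plan does not ask it.

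What is at stake is participant protection. Section 16 says that subjects gain no direct benefit, so an avoidable reaction has nothing to set against it. Section 10 provides for a single 45-minute visit and no follow-up, and Section 4 says that the monitoring board "will review the reported adverse events during testing". No later visit is planned at which a delayed reaction would be seen, so screening beforehand is the simplest protection available. The sweat volume and chloride comparisons are not at issue.

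**Working it through.** The plan states no figure on this point and no calculation settles it. The check is to set the sections side by side and count sites.

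**1. Does any criterion cover an earlier reaction?**

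- Skin exclusion: it covers skin disorders, and only those that could prevent forearm testing. A past reaction to a drug or a material, in someone whose forearm skin is now healthy, is not clearly a disorder and would not prevent the test.
- General health inclusion: a diagnosed drug or contact allergy could be read as a medical diagnosis. A self-reported reaction that was never diagnosed need not be.
- Medication criteria: these concern current use, not past reactions.
- Age, consent, family history, pregnancy and breastfeeding: not relevant.

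A formally diagnosed allergy may be caught, depending on how the screener reads the general line. A self-reported past reaction is not clearly caught by any line.

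**2. What is each subject exposed to, and where?** (Sections 6 and 7)

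| Site | Pilocarpine | Microneedle patch |
|---|---|---|
| Right forearm, iontophoresis | yes | no |
| Left forearm, active patch | yes | yes |
| Left forearm, control patch | no | yes |
| Sites exposed | 2 | 2 |

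There are three sites in all. Pilocarpine is at two of them and a patch at two; neither is at all three.

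**3. Which materials are involved?** Section 22 gives the patch ingredients as pilocarpine nitrate, poly(vinyl alcohol) and sucrose, with a second casting of polystyrene. Section 3 says that the needles dissolve in the skin. Adhesive tape is mentioned only for removing the patches from the mold (Sections 7 and 22). Whether adhesive touches the subject's skin is therefore an inference, and the point does not depend on it.

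**4. What does the Section 3 list establish?** It shows that allergic and skin reactions to pilocarpine are known. It gives no individual rate for rash, pruritus or allergic reaction, and it describes systemic effects from product labeling. It is not a rate for a short application to the forearm.

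**The case against.** The strongest reply is that known pilocarpine reactors will be scarce here. The clinical uses in the protocol are mainly dry mouth from radiation therapy or Sjögren syndrome, glaucoma and raised eye pressure, eye procedures, and sweat testing for cystic fibrosis. Subjects must have no known diagnosis, take no medication and have no family history of cystic fibrosis, so few are likely ever to have received the drug. That stands, and it makes the pilocarpine part of the gap small in practice. Sensitivity to patch or electrode materials does not depend on earlier pilocarpine use, and remains.

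A second reply is that the existing criteria already do the work. They do so in part, as shown above, but the result depends on the screener's reading. Appendix 10 (the iontophoresis product insert) is listed but not reproduced, so a contraindication there cannot be ruled out; Section 11 does not refer to it.

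A reader might also infer more than the documents support:

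- *That a sensitive subject is exposed at all three sites.* The control patch contains no pilocarpine, and the iontophoresis site has no patch.
- *That 1% to 10% of subjects would react.* That band is systemic labeling data among treated people, not a skin-application rate and not the share of volunteers with a known history.
- *That the chance of enrolling such a person can be calculated.* Any figure would rest on an assumed prevalence, and would give the chance of enrolling someone with a history, not of a reaction.
- *That one reaction among the first 10 subjects would distort the monitoring board's decision or force a redesign.* The board assesses the data independently, and redesign follows only if it reports safety concerns. No visible rule makes a single local reaction such a concern, and the charter (Appendix 11) is not reproduced. The control patch and the before-and-after photographs also help to separate drug, patch and iontophoresis effects.

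**Conclusion.** The gap is real and modest. Followed as written, Section 11 can admit a volunteer who knows of an earlier reaction to pilocarpine or to a patch or electrode material. That person would then have two pilocarpine sites and two patch sites, three in all, with no direct benefit and no follow-up visit.

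Its frequency cannot be given from the documents, and none is claimed; for pilocarpine itself it is probably low. The conclusion rests on two readings: that a self-reported past reaction is not necessarily a medical diagnosis, and that no restriction in the unreproduced appendices is applied at screening. It is a worthwhile participant-safety improvement because it changes who may be exposed at almost no cost. It does not bear on the validity of the primary or secondary comparison.

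**What to change.** Reconcile Section 11 with Sections 3 and 15. Add an exclusion for known hypersensitivity, or an earlier skin reaction, to pilocarpine or to any component of the patch or electrodes, including adhesive if it contacts the skin. Ask it as one screening question and record the answer in REDCap. The sponsor should state whether adhesive touches the skin, so that the question names the right materials.

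The cost is one line in the protocol, one screening question and a minor amendment for the ethics board, with no added test or procedure. The downside is that a few volunteers are turned away and the safety result applies to people without such a history. The report should say so.
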